#### **Clinical study:**

In a second study, dissociated phoria measurements with the app will be compared to the Modified Thorington (MT) test. Subjects will rest their head in a chin-head rest and the phone will be mounted 40 cm from the eyes. A 20/30 size letter attached below the phone camera lens served as a fixation point and controlled accommodation. The eyes will be alternately covered and then uncovered by an examiner with an occluder while the subject maintained the fixation. The app generated auditory tones to guide the examiner when to change the cover from one eye to the other. A higher-pitched tone was a cue to stop alternate cover and to uncover both eyes. The app recorded for 2 seconds after the final higher-pitched tone, resulting in 30 recorded frames. The app displayed the recorded frames and the user swiped through the frames to find and select the first frame after uncovering the eyes, which then was processed by the app to output the measurement value. Each subject was tested three times with the app in quick succession. Phoria also was measured using an MT near card (at 40 cm).

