## AIM 2:

Evaluate the strabismus app accuracy and feasibility in a clinical environment. Participants with strabismus will be tested with both the app and clinical methods and analyzed for levels of agreement and test-retest repeatability, satisfaction with the app evaluation, impact on symptoms, and perceived value.

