## **HYPOTHESES**:

For strabismus ranging from 1 to 30 prism diopters (target range), the optimized version of the app will provide measurements which are not significantly different from the ground truth (simulated strabismus) or clinical tests of eye alignment.

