Statistical Analysis Plan

Produced during publication of data

[name], [name], [name], [name], [name]; Development and Preliminary Evaluation of a Smartphone App for Measuring Eye Alignment. *Trans. Vis. Sci. Tech.* 2019;8(1):19.

August 1, 2019

Aim 1: Simulated Strabismus

The Hirschberg ratio (HR) for each subject was determined using data from all 13 fixation points by plotting the app measurement against the known angular deviation for each fixation point, and determining best fit of this scatter plot using linear regression. The slope of this function represents the individual's HR and the *y*-intercept is the individual's angle κ (the angle between the visual and optical axes, represented as κ).^{18,19} We measured the within-subject test–retest repeatability of the app in estimating the HR and κ using a Bland-Altman²⁰ plot to compute 95% confidence interval (CI) of the difference between two trials. Furthermore, we tested the accuracy of using a population average value of the HR by comparing the absolute gaze angles estimated by the app measurements and the true deviation of the fixation targets (via regression analysis using MATLAB; Mathworks, Natick, MA). The HR used for a subject was the average HR of the rest of the subjects.

Aim 2: Strabismus

Linear regression analysis was used to compare the app measurements of strabismus angle with cover test with prism neutralization CTPN measurements. Since the CTPN measurements were done at near fixation to facilitate direct comparison with the app measurements, corrections were made to the recorded CTPN values during data processing to account for the finite distance between the prism and center of rotation of the eye.²² We arrived at a value of the distance between prism and center of rotation of eye by assuming a population average value of 24 mm for axial length²³ and a back vertex distance of 10 mm.

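### Protocol and SAP do not match on the clinical comparison: the MT phoria procedure has no analysis, the CTPN regression has no stated procedure, and SAP Aim 2 omits agreement, mean difference and repeatability

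*Protocol*

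**What the plan says.** **Protocol.** The primary outcome is a comparison of the app with ground truth and with clinical tests. Aim 2 states: "Participants with strabismus will be tested with both the app and clinical methods and analyzed for levels of agreement and test-retest repeatability". The secondary outcomes define accuracy as a mean difference, for simulated and for measured strabismus alike, and list test-retest repeatability. The hypothesis, for 1 to 30 PD, is that the app gives "measurements which are not significantly different from the ground truth (simulated strabismus) or clinical tests of eye alignment". Objective 2 names CTPN, modified Thorington (MT) and Von Graefe as alternatives, joined by the word or. The eligibility criteria require strabismus for the clinical study.

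The Clinical study section then describes one comparison: "dissociated phoria measurements with the app will be compared to the Modified Thorington (MT) test". The phone is mounted at 40 cm, the head is in a rest, the eyes are alternately covered, and MT is read from a near card at 40 cm. "Each subject was tested three times with the app in quick succession".

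**SAP.** Under Aim 2 the only analysis is this: "Linear regression analysis was used to compare the app measurements of strabismus angle with cover test with prism neutralization CTPN measurements". The text continues "Since the CTPN measurements were done at near fixation to facilitate direct comparison with the app measurements" and then gives a correction for the distance from prism to centre of rotation. Under Aim 1, the repeatability of the Hirschberg ratio (HR) and angle kappa is assessed with a Bland-Altman "plot to compute 95% confidence interval (CI) of the difference between two trials". The SAP is headed "Produced during publication of data".

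**The concern.** App versus clinical tests is half of the primary outcome. The comparator with a procedure (MT) is not the comparator with an analysis (CTPN). The quantity measured also changes, from dissociated phoria in the Clinical study section to strabismus in Aim 2, the eligibility criteria and the SAP. A reader cannot tell which comparison answers the primary outcome, in whom, or under what viewing conditions.

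The protocol also names the quantities it wants from the clinical data, and the SAP provides a method for none of them. A closely fitting regression line is compatible with a constant or proportional bias, so it does not by itself bear out the hypothesis of no difference from clinical tests. The three repeat app readings, the only clinical repeat data described, have no analysis at all.

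**Working it through.** **Step 1. The two comparisons side by side.**

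| Element | MT | CTPN |
|---|---|---|
| Procedure for participants | Protocol, Clinical study | None; an option in Objective 2 and general clinic practice in Study Procedures |
| Quantity | Dissociated phoria | Strabismus angle |
| Fixation distance | 40 cm | Near; no figure in cm |
| App mode | Video with alternate cover | Not stated |
| App readings per subject | 3 | Not stated |
| SAP analysis | None | Linear regression; dependent variable not named |
| Mean difference or limits of agreement in SAP | None | None |
| Clinical repeatability in SAP | None | None |

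The single-picture mode at 30 cm in Study Procedures may be what was used with CTPN, but no text links the two. The Aim 1 Bland-Altman analysis concerns HR and kappa over two trials, so it cannot stand in for the last two rows.

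**Step 2. Does a regression supply the missing quantities?** The documents give no figure to reproduce, so this is an illustration.

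Inputs: the 1 to 30 PD range is from the hypothesis. The following are assumptions: a uniform spread over that range, unsigned angles, the app regressed on the reference, and error SD s = 2.8 PD. The 2.8 borrows the size of the preliminary figure in the protocol's Background, which is a measurable difference and not an SD.

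Model: app = a + b × reference + error. The reference has mean 15.5 and variance 29²/12 = 70.08.

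- R² = b² × 70.08 / (b² × 70.08 + s²)
- Mean difference = a + (b − 1) × 15.5
- SD of differences = √((b − 1)² × 70.08 + s²)
- Limits = mean difference ± 1.96 × SD

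Results with s² = 7.84:

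- No bias (a = 0, b = 1): R² = 70.08/77.92 = 0.90; mean difference 0; limits ±5.5 PD.
- Constant bias (a = 5, b = 1): R² = 0.90 again; slope 1, intercept 5; limits 5 ± 5.49, or −0.5 to 10.5 PD.
- 20% under-reading (a = 0, b = 0.8): R² = 44.85/52.69 = 0.85; slope 0.8; mean difference −0.2 × 15.5 = −3.1 PD; SD = √(2.80 + 7.84) = 3.26; limits −9.5 to 3.3 PD.

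For s from 1.5 to 4 PD, R² with the 5 PD bias runs from 0.97 to 0.81, the same as with no bias.

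**Step 3. Signed angles.** If inward and outward deviations are balanced over ±1 to 30 PD, the mean is 0 and the variance is 70.08 + 15.5² = 310.3. The same 20% under-reading then gives R² = 198.6/206.5 = 0.96, mean difference 0, SD = √(12.41 + 7.84) = 4.50 and limits of about ±8.8 PD. So the mean difference alone can also hide a proportional bias.

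**Step 4. Error in the reference.** If the app is regressed on CTPN and CTPN has error SD r, an unbiased app has expected slope variance/(variance + r²). With r = 2.8 PD (assumed) this is 70.08/77.92 = 0.90, with intercept 15.5 × (1 − 0.899) = 1.6 PD, for unsigned angles. For balanced signs it is 310.3/318.2 = 0.975. For r from 1.5 to 4 PD the slope runs from 0.97 to 0.81 (unsigned) or 0.99 to 0.95 (balanced).

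**The case against.** The strongest reply is that regression is not blind to bias. In the illustration the 5 PD bias appears as an intercept of 5 and the under-reading as a slope of 0.8; Aim 1 of the same SAP interprets slope and intercept; and the SAP never names R-squared as its criterion. This stands. A reader might infer that the planned regression could not detect bias, and the documents do not support that. What remains is that Aim 2 does not say how slope and intercept will be judged, and that neither gives limits of agreement.

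A reader might also infer that reference error must pull the SAP's slope below 1. That depends on regressing the app on CTPN, and the SAP names no dependent variable. With the axes reversed, it is app error that would attenuate the slope. The size also depends on the sign convention, as Step 4 shows.

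Other replies stand in part. A regression nominally meets a primary outcome that asks only for a comparison, and the protocol itself defines the mean difference; the omission is in the SAP. Objective 2 permits a choice among tests, but that does not explain why the test with a procedure is not the one analysed. A SAP written at publication may explain the mismatch without removing it.

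**Conclusion.** The mismatch holds on a plain reading and rests on no assumption: MT has a procedure without an analysis, CTPN has an analysis without a participant-level procedure, the endpoint differs between them, and three promised clinical quantities (agreement, mean difference, repeatability) have no method in SAP Aim 2. It must be fixed, because half of the primary outcome cannot be interpreted as written.

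The numerical sizes are illustrative only. They rest on an assumed uniform spread, an assumed error SD and an assumed regression direction, and they shift with the sign convention: the mean difference for a 20% under-reading is −3.1 PD with unsigned angles and 0 with balanced signs.

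Two stronger readings go too far. A reader might infer that the three repeat readings can deliver the repeatability promised in Aim 2. They are phoria readings in quick succession with a head rest and a mounted phone, so they show same-session repeatability of that mode and not repeatability in strabismus. A reader might also infer that the CTPN measurements lacked a procedure in practice, or that MT results were withheld. The documents show only that these details are not written down.

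**What to change.** 1. Reconcile Aim 2, Objective 2, the hypothesis, eligibility, outcomes, the Clinical study section and SAP Aim 2. For each clinical comparison actually made, state participants, endpoint (phoria or strabismus), reference test, fixation distance, app mode and number of app readings. Say so if a comparison was not made. Von Graefe needs covering only if it was used.
2. In SAP Aim 2 keep the CTPN regression, name the dependent variable, and report slope and intercept with 95% CIs. Add, separately for each comparator, the signed mean difference (app minus reference; nasal positive and temporal negative, as in the protocol's Figure 2 caption) with 95% CI and 95% limits of agreement. Plot differences against averages, and use regression-based limits if the difference changes with size.
3. For MT, state whether the first or the mean of the three readings is used. A mean of three carries within-subject variance Sw²/3 and a single reading carries Sw², so if the mean is used, add (1 − 1/3) × Sw² = (2/3) × Sw² to the variance of the differences. The limits then apply to a single reading.
4. Report Sw and the repeatability coefficient 1.96 × √2 × Sw = 2.77 × Sw for the three readings, described as same-session repeatability of the phoria mode under head-rest conditions. Report strabismus repeatability only if repeat app readings were taken in that comparison; otherwise state that it was not assessed.
5. Label the added analyses post hoc, given the SAP's heading.

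Cost: amended text and a little more analysis of values the documents already describe, with no new cohort or test. The additions carry only post hoc weight and cannot restore prespecification.

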## **STUDY PROCEDURES**

Using a conventional smartphone with a high resolution rear camera and flash (for example, Samsung Galaxy S4 and above; Samsung, Seoul, South Korea, and iPhone 5 and above; Apple, Cupertino, CA), the EyeTurn app automatically detects the difference in corneal reflection position relative to the eye center (based on fitting a curve to the limbus boundary) to calculate ocular misalignment, and provide an objective measure of eye deviation from the captured image

of the patient's eyes (Fig 1). The captured images are processed entirely within the smartphone using custom image processing algorithms, and the eye deviation measurements are displayed on the screen usually within a couple of seconds. We use iris center (center of the eye, or the center defined by the limbus curve) instead of pupil center as the reference for computing the corneal reflection decentration, as it has been reported to be a more robust reference for measuring ocular alignment, especially when computing binocular differences (Barry JC, Backes A 1997). Also, for darker iris colors, the limbus boundary is better-delineated than the pupil boundary in visible spectrum images captured by a typical smartphone camera. The corneal reflection decentration distance is converted to prism diopters (D) using an HR in the range of previously reported values (Jagini, 2014).

Figure: 1 The EyeTurn app for measurement of eye deviations. (Left) Features detected by the app via automatic image processing: limbus boundary denoted by a green circle, its center denoted by a green cross, and the corneal reflection due to the flash denoted by a red dot. The distance between the eye center and corneal reflection, shown as 'd', is compared between the two eyes to detect eye deviation. (Right) To measure the eye alignment using a single picture, the phone is held 30 cm from the eyes of the subject and a picture is taken as the subject fixates binocularly. This mode of operation is well suited for measuring or screening for manifest eye deviation. Permission to publish photograph was obtained via a signed consent to publish document.

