The app offers various operating modes through which the eve deviation can either be measured monocularly or binocularly. Additionally, the app also allows dissociated measurement, for example to measure intermittent strabismus condition or phoria, where the deviation between the eyes is not manifest. In clinic, measurement under dissociated conditions is done by performing either cover-uncover or alternate- cover tests with prisms (CTPN). One key feature of the app is the ability to measure eye deviations under dissociated conditions without the need for prism neutralization. In this operational mode, the examiner presses a button to record a video, while the patient fixates on a target binocularly. The patient's binocular fusion is broken in the traditional manner by either cover-uncover (of one eye) or alternate cover (involving both eyes). The examiner ultimately uncovers one eye, and the app records this entire event as a video sequence (Fig. 2). The user is prompted with audio tones to assist in the timing of the cover- uncover. The video frame just after uncovering an eye can be selected for processing the maximum dissociated eye deviation. Due to the high framerate of video capture (30 Hz), we can measure the deviation before a recovery vergence eye movement can be initiated. Figure 2b shows an example of the eye movement trace obtained when performing the alternate cover test, with a smartphone recording the video of this event.

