Figure 2. Cover testing mode for dissociated measurements using the app. (Top row) Alternating cover–uncover test using the video-based cover test mode. This novel operational mode can be used for dissociated measurements. The examiner alternately covers the eyes (first two images on top row). The frame with both eyes uncovered (third image on the top row) is selected for automatic processing by the app for measurement of the eye deviation. (Bottom row) Eye movement trace after offline processing of the video of the alternate cover test shows the movements of the eyes after the cover is removed. Negative values show temporal deviation (outward), whereas positive values show nasal deviation (inward). There is a brief duration after removing the cover during which the deviation can be measured (highlighted by the oval gray zone). It should be noted that the eye movement trace in this figure was generated by processing the video recorded by the smartphone on a desktop computer using the same image processing software used in the app, but may be included as part of the app in the future. Permission to publish photograph was obtained via a signed consent to publish document.

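### In the video cover-test mode the app user picks the frame by hand, and no test order or masking is written down to separate that choice from earlier app values or the Modified Thorington result

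*Protocol*

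**What the plan says.** The Protocol's Clinical study section compares dissociated phoria measured by the app with the MT near card. After alternate covering, the recording appears on the phone as single images: "the user swiped through the frames to find and select the first frame after uncovering the eyes". Only after that choice does the app compute a value, from the chosen image. The general description of the app under STUDY PROCEDURES adds that "the eye deviation measurements are displayed on the screen usually within a couple of seconds". On repeats, the Clinical study section says: "Each subject was tested three times with the app in quick succession".

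The frame to be used is described in three places, in similar but not identical terms:
- The STUDY PROCEDURES text refers to the frame just after one eye is uncovered and ties it to the largest deviation under dissociation.
- The Figure 2 legend says: "The frame with both eyes uncovered (third image on the top row) is selected for automatic processing by the app". It also refers to a short interval after the cover is removed in which the deviation can be measured.
- The Clinical study section uses the first frame after the eyes are uncovered.

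Neither document says who operates the app and who does the MT test, in which order they are done, whether either person is masked to the other's result, or whether a frame may be re-selected once its value is seen.

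**The concern.** A person chooses the input that fixes each reading, and on this description may already know the previous reading, and perhaps the reference result, when choosing. A frame choice that leans towards a remembered app value pulls the repeats together. One that leans towards a known MT value pulls the app towards the reference. Both errors favour the app, and neither shrinks as more subjects are added.

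Two stated outcomes are exposed: the app-versus-clinical-test part of the primary outcome, as far as it rests on MT, and test-retest repeatability, a secondary outcome. The SAP would not reveal the problem, because it mentions neither the MT comparison nor the three repeats.

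**Working it through.** **1. The one stated figure.** The Clinical study section says: "The app recorded for 2 seconds after the final higher-pitched tone, resulting in 30 recorded frames". STUDY PROCEDURES gives a capture rate of 30 Hz.
- Frames expected: 2 s × 30 Hz = 60, against 30 stated.
- Rate implied by the stated count: 30 / 2 s = 15 Hz.
- Time per frame: 1000/30 = 33 ms at 30 Hz, or 1000/15 = 67 ms at 15 Hz.

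The figures do not reconcile. At the lower rate, a slip of one frame allows twice as long for the eyes to move.

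**2. Where the hand choice enters.**
- Phoria comparison with MT (Clinical study): the frame is chosen by the user.
- Ground-truth study (fixed targets, chin rest): no frame selection is described.
- SAP Aim 1 repeatability (two trials; Hirschberg ratio and angle κ): built on the fixed-target data, so not exposed.
- SAP Aim 2 (regression against the cover test with prism neutralization): the SAP does not say whether hand-selected video frames were used.

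**3. How large it could be.** The documents give no reading error, no number of plausible frames and no between-frame correlation, so all three are assumptions.

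Model: the first reading has error e₁ with SD σ. The second video offers k plausible frames with errors f₁…f_k, each with SD σ, pairwise correlation ρ, and independent of e₁.
- Choice made without regard to value: SD(f − e₁) = σ√2, so the ratio to the masked SD is 1.00.
- Value-guided choice: take the frame with the smallest |f_j − e₁|, and compute SD(difference) / (σ√2).

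Results from 1,000,000 simulated pairs per row, with guided choice on every repeat:

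| ρ | k = 2 | k = 3 | Fall in SD |
|---|---|---|---|
| 0.5 | 0.76 | 0.65 | 24% and 35% |
| 0.8 | 0.85 | 0.78 | 15% and 22% |
| 0.95 | 0.93 | 0.89 | 7% and 11% |

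If the guided choice occurs in only some readings, the fall is smaller. At half of readings it is 7 to 10% (ρ = 0.8) or 11 to 16% (ρ = 0.5). At one reading in five it is about 3 to 4% (ρ = 0.8). The repeatability coefficient, being a multiple of this SD, shrinks by the same share.

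**4. Agreement with MT.** The same ratios apply to the SD of app minus MT if the MT result is known first, the two methods have equal error SD, and there is no systematic difference between them. A simpler model sets the recorded value to (1 − w) × own reading + w × MT. Then app minus MT is (1 − w) times its masked value, and the limits of agreement narrow by exactly w. That shows direction only, since w is whatever one assumes.

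**The case against.** The strongest objection is about mechanism. The value is produced after the frame is chosen, and swiping shows images, not deviations. To take the frame closest to a remembered value, the user would have to process several frames and keep one, or judge small shifts of the corneal reflection by eye. The documents describe neither. The rule is also ordinal (the first frame), the Figure 2 legend requires both eyes uncovered, and the measurement is automatic once the frame is fixed. STUDY PROCEDURES says the deviation is caught before a recovery movement can begin, so neighbouring early frames may be very highly correlated, which points to the low end of the table or below it.

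This stands as a limit on size and likelihood. It does not remove the concern: the three descriptions of the frame leave room at the margin, re-selection is not ruled out, and an earlier value can be remembered.

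A reader might also infer one of three stronger claims, none of which the documents support:
- That repeatability is overstated by 15 to 35%. Those figures require value-guided choice on every repeat, which is not described.
- That the whole primary outcome is biased. The ground-truth comparison involves no frame selection, and the SAP's Aim 2 analysis is against a different clinical test.
- That the user knew the MT result. The text mentions MT after the app readings but states no order, and masking may have been used without being written down.

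**Conclusion.** The point holds as a gap in measurement procedure, confined to the video cover-test mode and the MT comparison. An operator's choice feeds the app value, and no written safeguard separates that choice from earlier values or from the reference. Any effect through this route would be in the app's favour. Its size cannot be determined from the documents: zero if frames are chosen without regard to value, 7 to 11% of the test-retest SD at correlation 0.95, and 15 to 35% only as a hypothetical upper scenario (2 or 3 plausible frames, correlation 0.8 to 0.5, guided choice every time). The SAP defines no analysis of the three repeats or of MT, so the bias would fall on the Protocol's outcomes and not on a specified SAP estimate. This justifies a cheap improvement; it is not evidence that results were distorted.

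**What to change.** Set the order of work in the Clinical study section:
1. Record all three videos.
2. In each, select and lock the first frame with both eyes uncovered, before any value is displayed.
3. Allow no re-selection after a value has been seen, or log and report every one.
4. Complete this before the MT result is taken or seen, and withhold the app values until MT is recorded.

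Also state who operates each test, use one definition of the frame throughout, and reconcile the 2 s, 30 Hz and 30-frame figures.

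The cost is a few minutes' delay and possibly a minor app change to defer the display. No extra reader is needed. Automatic frame selection by the software would be a further option, but it needs development and is not part of the cheap fix.

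The procedure is written partly in the past tense and the SAP says it was produced during publication, so reordering may come too late for some data. For those, report the order, operators and masking actually used. If the videos were kept, which the documents do not state, the frames could be re-selected with values hidden.
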